7.0 STUDY PLAN

7.1 Overview

Parents/Guardians who have previously contacted our program and have a child who may meet eligibility criteria for this study will be notified that this study is available. After initial contact, parents/guardians of potential research participants will have an initial phone interview with study personnel to describe the study, verify basic eligibility criteria, and confirm their interest in participation. The participant's eligibility will then be screened through review of medical records, video, laboratory testing, and imaging under a separate screening protocol.

Once all screening is complete and the patient is likely to meet study criteria, a suitable

unrelated donor CB unit will be identified at the Carolinas Cord Blood Bank, or other accredited cord blood bank. The CB unit will be screened as described in section 6. Participants will then travel to Duke for their first visit. On day 1, written informed consent will be obtained. Patient eligibility will be confirmed by a physical observation and verification of cerebral palsy diagnosis and GMFCS level. If no exclusion criteria are realized, the participant will be randomized to a treatment arm. During their first visit, all participants will have physical therapy evaluations, and a subset of patients will undergo brain MRI. Participants will have study infusions as determined by their assigned treatment arm (at baseline only for AlloCB; at 12-months only for Natural History; at baseline, 3-, and 6-months for MSCs). Participants will be evaluated the day after each infusion. All participants will return to Duke six (motor assessments) and 12 months (motor assessments and brain MRI) after the baseline visit. Participants on the MSC arm will also return at three months for an hCT-MSC infusion. A remote safety assessment will be performed via phone or email at 24 months post-infusion.

7.2 Patient Screening

Initial patient screening will be conducted with informed consent under a separate protocol and will include a review of medical records, videos, and initial laboratory testing. If no exclusion criteria are identified, informed consent will be obtained, and the patient will be randomized to a treatment arm. If indicated (AlloCB and Natural History arms), an unrelated donor CB unit will be identified at the Carolinas Cord Blood Bank, or other accredited cord blood bank. Participants will travel to Duke for initial evaluation. Evaluations and treatments will be conducted in the outpatient setting. A physical exam and baseline GMFCS assessment will be conducted to confirm eligibility, and the participant undergo the remainder of the study evaluations.

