5.4 Research Participant Recruitment and Screening

Patients may be recruited through IRB-approved advertising for the study on the websites of CB banks, parent sponsored websites, the NMDP website, selected cerebral palsy societies, local medical providers, and through a record of inquiries for previous studies (brain injury database. Separate IRB approval will be obtained for any advertisements.

Screening for this study is conducted under a separate, IRB-approved screening protocol (Pro00063563). Under this protocol, after written informed consent is obtained from a parent/guardian, the patient's medical records, videos, and results of brain imaging are obtained and reviewed. The medical review is conducted by a team of pediatric nurses, nurse practitioners, and physicians to identify the presence of any exclusion criteria. If no exclusion criteria are identified, screening labs are performed and a search may be conducted to identify a suitably matched CB unit (see section 6.1).

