7.3 CB Unit Selection

For participants randomized to the AlloCB and Natural History arms, an allogeneic unrelated donor CB unit will be identified at the Carolinas Cord Blood Bank, or other accredited cord blood bank. HLA typing will be obtained on the patient, and the best available HLA-matched CB unit with a pre-cryopreservation nucleated cell dose $\geq 12 \times 10^7$ cells/kg will be chosen. We target CB units that are at least 12×10^7 cells/kg, however, we will accept units that are at least 10×10^7 cells/kg. When possible, at least 1 match at each HLA loci will be prioritized. An Rh negative CB unit will be selected for Rh negative female participants to avoid Rh sensitization in young females.

Once a suitable allogeneic CB unit has been deemed an acceptable match, a sample of the CB unit will be tested for potency in the Duke STCL. If results of these tests are satisfactory, the CB unit will be delivered to the Duke STCL in the frozen state.

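### Section 7.1 and Sections 7.2/7.3 order consent, unit search, on-site eligibility and randomisation incompatibly; following 7.2 puts baseline inputs to the primary endpoint after open-label allocation

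*Combined protocol and SAP*

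**What the plan says.** **Section 7.1 (Overview).** After remote screening, a CB unit is found for any child likely to qualify: "The CB unit will be screened as described in section 6. Participants will then travel to Duke for their first visit". Consent is taken on day 1 of that visit. Then "Patient eligibility will be confirmed by a physical observation and verification of cerebral palsy diagnosis and GMFCS level". Only after that: "If no exclusion criteria are realized, the participant will be randomized to a treatment arm". On motor testing it adds "During their first visit, all participants will have physical therapy evaluations", without placing this before or after randomisation.

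**Section 7.2 (Patient Screening).** When remote review shows no exclusion, "informed consent will be obtained, and the patient will be randomized to a treatment arm". A unit is then sought for the AlloCB and Natural History arms, and the family travels. On site, "A physical exam and baseline GMFCS assessment will be conducted to confirm eligibility", followed by the other study evaluations.

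**Section 7.3 (CB Unit Selection)** agrees with 7.2: "For participants randomized to the AlloCB and Natural History arms, an allogeneic unrelated donor CB unit will be identified".

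**Related text**
- Section 5.4 makes an earlier search optional: "a search may be conducted to identify a suitably matched CB unit".
- Sections 4.1 and 8.1 describe an open-label trial with randomisation stratified by GMFCS (I/II or III/IV) and etiology.
- Section 4.3 computes the expected 12-month score from age, GMFCS level and GMFM-66 at entry.
- Section 8.6.1 evaluates the primary endpoint in everyone randomised, by assigned arm.
- Section 5.5 counts a child taken off study before the CB infusion as non-evaluable and replaceable. Section 9.6 lets the sponsor replace any undosed subject.

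**The concern.** The two sequences describe different trials at the point where randomisation has to be protected. Allocation is not masked. Under 7.2, whoever confirms eligibility, assigns the GMFCS level or scores the baseline GMFM-66 may do so when the family and staff already know the arm. Two of those baseline values determine the expected score and so enter the primary endpoint directly. One of them, GMFCS, is also meant to define the randomisation stratum.

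Under 7.2, children found unsuitable on site, or AlloCB children for whom no unit is found, are already randomised. The plan gives two possible treatments for them, and the number affected could differ between arms.

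**Working it through.** No figure in the plan is in dispute, so the check is a comparison of text, followed by tracing what depends on the order.

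**1. The two sequences**

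| Step | Section 7.1 | Sections 7.2/7.3 |
|---|---|---|
| Remote screening | Before randomisation | Before randomisation |
| Consent | Day 1, after travel | After remote screening, before travel |
| CB unit identified | Before travel, arm unknown | After randomisation, two arms only |
| In-person eligibility and GMFCS | Before randomisation | After randomisation and travel |
| Baseline GMFM-66 | First visit; order not stated | After randomisation |

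Section 7.2 cannot be read as an unordered list. A search confined to two arms requires a known arm, and 7.3 says so explicitly. For GMFM-66, 7.2 puts the remaining evaluations after the GMFCS assessment, and table 7.9 schedules GMFM-66 at the baseline visit.

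**2. Whether another section settles it**
- Section 5.4 permits an early search but does not require one, so it fits both.
- Section 6.1 requires HLA typing of all potential participants, and table 7.9 schedules it at screening. This is compatible with 7.1, and also with 7.2, where the arm is still unknown at that stage.
- Table 7.9 lists unit potency and confirmatory typing at screening only under the two CB arms. This fits 7.2/7.3 better but does not state when randomisation occurs.

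None of these resolves the order.

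**3. How baseline enters the endpoint.** Let Y0 and Y12 be the observed GMFM-66 scores and E12 the expected 12-month score, a function of baseline age, GMFCS and Y0. The endpoint is

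(Y12 − Y0) − (E12 − Y0) = Y12 − E12.

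Baseline GMFM-66 and GMFCS therefore act only through E12. If scoring of either shifted with knowledge of the arm, that arm's mean E12 would shift, and its mean endpoint would move by the same amount in the opposite direction. How far E12 moves per point of Y0 depends on reference curves that the documents cite but do not reproduce.

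**4. Losses after allocation under 7.2.** A child found ineligible on site is randomised and so belongs to the population in 8.6.1. Sections 5.5 and 9.6 allow an undosed child to be treated as non-evaluable or replaced. Lack of a CB unit cannot affect the MSC arm. It affects AlloCB at baseline. Natural History is infused only at 12 months, so its 12-month endpoint is much less exposed.

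**5. Numbers in the plan.** The plan's iteration reproduces: N = (t × 5.16/2)² gives 29.16, 27.93 and 28.02 with unrounded t quantiles, rounding to 29, 28 and 28 as tabulated. At 30 per arm the half-width is 2.045 × 5.16/√30 = 1.93. Nothing here changes these figures. With 90 evaluable children at 1:1:1, each arm has 90/3 = 30.

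**The case against.** The strongest reply is that 7.1 is headed as an overview and the conflict is loose drafting. Remote screening precedes allocation in both versions, so only final confirmation is at issue. GMFM-66 is a standardised instrument with totals computed by a program, and no section says that baseline raters know the arm. All of that is fair. It limits the likely harm but does not tell staff which order to follow, and no section says that raters are masked.

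Several stronger readings are tempting, and the documents do not support them:

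- *That post-allocation GMFM-66 is purely a 7.2 problem.* Section 7.1 also mentions motor testing after its randomisation sentence without fixing the order. Adopting 7.1 unchanged would secure eligibility and GMFCS but not GMFM-66.
- *That ineligible or untreated children must end up in an arm's estimate.* Section 8.6.1 points that way, but 5.5 and 9.6 allow replacement. What the text supports is two possible treatments, not a certain one. Section 5.5 also does not list day-1 ineligibility or lack of a unit among its removal criteria, so applying it to these children is itself an inference.
- *That a corrected GMFCS level biases an arm.* It mis-stratifies only if it crosses between II and III. That costs balance and does not by itself bias an arm mean.
- *That bias occurred or can be quantified.* The documents do not show which order was used. They give no day-1 ineligibility rate, no unit-search failure rate and no baseline scoring shift.

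**Conclusion.** The contradiction holds on the text alone: 7.1 and 7.2/7.3 differ on consent, unit identification, in-person confirmation and randomisation, and no other section decides between them. If 7.2 is followed, confirmation of eligibility and GMFCS, and baseline GMFM-66, follow open-label allocation for every randomised child. If 7.1 is followed, the first two precede it and GMFM-66 is unspecified.

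The consequence is an avoidable risk of bias in each arm's observed-minus-expected mean, and ambiguity about who is analysed. Its size cannot be derived from the documents, so none is given. The sample size and planned precision are unaffected. The 12-month assessment is open-label under either order, and resolving this point does not change that. It should be fixed, but it does not undermine the design as a whole.

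**What to change.** State one order in Sections 7.1, 7.2, 7.3 and 7.9: consent; on-site confirmation of eligibility, GMFCS and baseline GMFM-66, all completed and recorded; then stratified randomisation. Specifically:

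- in 7.2, move the randomisation sentence after the GMFCS assessment;
- in 7.1 and 7.9, state that baseline GMFM-66 precedes randomisation;
- in 7.3, align the text so that a suitable unit is identified before allocation, as 7.1 already describes and 5.4 permits.

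**Cost.** The change is protocol wording and visit-day sequencing. A unit must be identified for about 30 children later assigned to MSC, who will not use it. Section 7.1 has the unit screened as in Section 6, and Section 6.1 includes segment testing and transfer of the designated unit before arrival, so that work might also be done for these children. Product preparation would follow day-1 allocation. The sponsor should decide how much testing and transfer happens before allocation and reconcile 6.1, 7.1, 7.3 and 7.9 accordingly.

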7.3 CB Unit Selection

For participants randomized to the AlloCB and Natural History arms, an allogeneic unrelated donor CB unit will be identified at the Carolinas Cord Blood Bank, or other accredited cord blood bank. HLA typing will be obtained on the patient, and the best available HLA-matched CB unit with a pre-cryopreservation nucleated cell dose $\geq 12 \times 10^7$ cells/kg will be chosen. We target CB units that are at least 12×10^7 cells/kg, however, we will accept units that are at least 10×10^7 cells/kg. When possible, at least 1 match at each HLA loci will be prioritized. An Rh negative CB unit will be selected for Rh negative female participants to avoid Rh sensitization in young females.

Once a suitable allogeneic CB unit has been deemed an acceptable match, a sample of the CB unit will be tested for potency in the Duke STCL. If results of these tests are satisfactory, the CB unit will be delivered to the Duke STCL in the frozen state.

7.4 Study Product Infusion

On the day of infusion, CB cells or hCT-MSC product will be prepared by the STCL and provided for infusion of the patient in the outpatient clinic under the supervision of the study team and Pediatric Blood and Marrow Transplant Program staff. A peripheral IV will be placed by clinical staff, anesthesia or a member of the study team. Prior to the study infusion, premedications (Benadryl and Solumedrol) will be administered. CB cells will have a four-hour expiry at room temperature post-thaw.

Allo CB infusion will be given over approximately 5-25 minutes and hCT-MSC infusions over 30-60 minutes using standard practices. The child will receive 1-1.5x maintenance

IV fluids as described below and be observed in the clinic for a minimum of one hour after the infusion. Patients will be discharged from clinic after at least one hour providing all vital signs are at their baseline and they are awake and asymptomatic with no evidence of toxicity. Patients will be evaluated by study staff the day after the infusion to assess for any infusion-related adverse reactions or complications. A phone call to parents/guardians by study staff to assess safety of the infusion will be conducted two weeks after the infusion.

Maintenance IV Fluid Rate (Holliday-Segar Method from Harriet Lane Handbook)Body weight:mL/kg per day1st 10 kg100divided by 24hr/day2nd 10 kg50divided by 24 hr/dayeach add'l kg20divided by 24 hr/day

If a patient has evidence of illness on the day of planned infusion, including but not limited to fever >38.5° C, vomiting, diarrhea, or respiratory distress, the infusion will be postponed.

7.5 Care During Unexpected Events

In the event that a patient develops signs or symptoms of anaphylaxis including urticaria, difficulty breathing, cough, wheezing, or vomiting during their CB infusion, the infusion will be terminated and appropriate medical therapy initiated.

7.6 Motor Assessments

Gross Motor Function Measurement-66 (GMFM-66): The GMFM-66 is a standardized observational instrument designed and validated to measure change in gross motor function over time in children with cerebral palsy. Developmental curves of expected progression have been published for children ages 2 – 12 years,^{64,116} allowing for the calculation of future expected scores based on the baseline age, GMFCS level, and GMFM-66 score. The GMFM-66 consists of 66 items, divided into five categories: lying and rolling, sitting, crawling and kneeling, standing, and walking, running, and jumping. Each item is scored on a four-point Likert scale. The GMFM-66 is a subset of the GMFM-88, which contains an additional 22 items, primarily in the lying and rolling category. Both measures have been validated in children with cerebral palsy from 5 months to 16 years of age. A 5-year old child without motor disabilities is able to reach the maximum score.¹¹⁷ A computer program, the Gross Motor Ability Estimator, is used to calculate the GMFM-66 total scores. The primary endpoint of this study is the difference between a child's actual and expected changes in GMFM-66 score 12 months after the initial study infusion. Control (placebo) and treated patients will be compared. When possible, the entire GMFM-88 will be performed, and subsets may be analyzed as exploratory endpoints.

Peabody Developmental Motor Scales (PDMS-2): The PDMS-II is a standardized assessment of early childhood motor development that evaluates both gross and fine motor skills. It is designed for children from birth through 5 years of age. The assessment is composed of six subtests that measure interrelated motor abilities that develop early in life (i.e., reflexes, stationary, locomotion, object manipulation, grasping, and visual-motor integration). Gross Motor Quotient, Fine Motor Quotient, and Total Motor Quotient composite scores are obtained. For this study, the Gross Motor Quotient will be obtained and analyzed as a secondary endpoint.

7.7 Functional Assessment

Pediatric Evaluation of Disability Inventory-Computer Adaptive Test (PEDI-CAT): The PEDI-CAT measures abilities in three functional domains: Daily Activities, Mobility, and Social/Cognitive. The computerized adaptive version is intended to provide an accurate and precise assessment of a child's abilities while increasing efficiency and reducing respondent burden by utilizing item response theory statistical models to determent which items are assessed within each domain based on responses to prior items.

7.8 Imaging Assessments

Participants' brain imaging obtained previously as standard of care will be reviewed by a member of the Brain Imaging Analysis Center (BIAC) team to determine if accurate anatomical image parcellation would be likely on a brain MRI. Those participants for whom usable data is likely to be obtained (estimated as approximately two-thirds of eligible participants) will undergo brain MRI with diffusion tensor imaging (DTI). Diffusion weighted images will be acquired on a 3 Tesla GE scanner (Waukesha, WI). *T1-* weighted images will be obtained with an inversion-prepared 3D fast spoiled-gradient-recalled (FSPGR) pulse sequence. These images will be analyzed to obtain measures of whole brain connectivity.

7.9 Required Evaluations

	Time Points#					
	Screening	Baseline	3 months	6 months	12 months	24 months
All Participants						
CBCD*, CMP*, Type & Screen*, Patient HLA typing	Х					
Patient DNA sample for chimerism		Х				
CBCD*, CMP*, Type & Screen*, Direct Coombs, HLA Antibody Screen (PRA), Immune Reconstitution Panel, Humoral Immune Profile		х			х	
Motor Assessments (GMFM-66, PDMS-2)		Х		Х	Х	
Brain MRI^		Х			Х	
Functional Assessment (PEDI-CAT)		Х		Х	Х	
Safety Assessment – remote						Х
AlloCB Participants						
CBU potency; HLA confirmatory typing	Х					
History & Physical		Х		Х	Х	
Donor Referral Panel		Х				
CBU: TNCC, viable CD34 ⁺ count, CFU, sterility culture, donor DNA sample for chimerism		х				
Safety Assessment – in-person, day after infusion		Х				
Natural History Participants						
CBU potency; HLA confirmatory typing	Х					
History & Physical		Х		Х	Х	
Donor Referral Panel					Х	
CBU: TNCC, viable CD34 ⁺ count, CFU, sterility culture, donor DNA sample for chimerism					Х	
Safety Assessment – in-person, day after infusion					Х	
MSC Participants						
History & Physical		Х	Х	Х	Х	
Donor Referral Panel		Х				
CBCD, CMP			Х	Х		
Safety Assessment – in-person, day after infusion		Х	Х	Х		
*CBCD and CMP may be obtained at baseline or within 6 month ^Brain MRI will be performed on patients with eligible screening		nt				

*Safety and return assessments should be performed within a month of the indicated time point.

Abbreviations: CBCD-Complete Blood Count and Differential, CMP-Complete Metabolic Panel, HLA-Human Leukocyte Antigen, GMFM-66-Gross Motor Function Measure-66, PDMS-2-Peabody Developmental Motor Scale-2, MRI-Magnetic Resonance Imaging, CBU-Cord Blood Unit, TNCC-Total Nucleated Cell Count, CFU-Colony Forming Units

8.0 STATISTICAL CONSIDERATIONS

8.1 Study Design

This study is a phase I/II, prospective, randomized, open-label trial designed to provide interval estimates of the 12-month change in motor function after treatment with AlloCB and hCT-MSC, provide additional data to the clinical trials community on the natural history of the motor function in CP over short-term (less than 1 year) time periods relevant to conduct of clinical trials, and assess the safety of repeated doses of hCT-MSC and a single dose of AlloCB in children with cerebral palsy.

Children ages 2-5 years with cerebral palsy due to hypoxic ischemic encephalopathy, stroke, or periventricular leukomalacia will be eligible to participate. All participants will ultimately be treated with an allogeneic cell product at some point during the study. Participants will be randomized (1:1:1) to one of three arms: (1) the "AlloCB" arm will receive one allogeneic CB infusion at the baseline visit; (2) the "MSC" arm will receive three hCT-MSC infusions, one each at baseline, three months, and six months; the "natural history" arm will not receive an infusion at baseline but will receive an allogeneic CB infusion at 12 months. The occurrence of adverse events will be evaluated at 3, 6, 12, and 24 months post-randomization in all participants. Motor function outcome measures will be assessed at baseline, six-months, and one-year time points in all participants. Duration of study participation will be 24 months from the time of the baseline visit. Randomization will be stratified by GMFCS Level (I/II or III/IV) and etiology of CP (Stroke vs. Other).

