2.11 Study Design

This study is a phase I/II, prospective, randomized, open-label trial designed to assess the effect size of change in GMFM-66 score in subjects treated with hCT-MSC or allogeneic CB and assess the safety of repeated doses of hCT-MSC in young children with cerebral palsy. Children ages 2-5 years with cerebral palsy due to hypoxic ischemic encephalopathy, stroke, or periventricular leukomalacia may be eligible to participate. All participants will ultimately be treated with an allogeneic cell product at some point during the study. Participants will be randomized to one of three arms: (1) the "AlloCB" arm will receive one allogeneic CB infusion at the baseline visit; (2) the "MSC" arm will receive three hCT-MSC infusions, one each at baseline, three months, and six months; (3) the "natural history" arm will not receive an infusion at baseline but will receive an allogeneic CB infusion at 12 months. All participants will have an initial clinical evaluation to verify and classify the diagnosis of cerebral palsy and determine eligibility. They will return for study visits an additional two (AlloCB and natural history arms) or three (MSC arm) times. Outcome measures, described in detail in section 7.6, will be assessed at baseline, six-months, and one-year time points. Additional safety endpoints will be assessed remotely for 12 months after the final in-person visit.

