6.6 Safety Follow-up

On Day 1 following the infusion, the participant will be seen by study staff to assess for any infusion related adverse reactions or complications. At ~2 weeks post-infusion, a member of the study team will contact the parent or guardian via phone or email to assess patient status and any adverse events. In-person safety assessments will occur at each study visit. In addition, a questionnaire (see Appendix 1) will be administered at 6, 12, and 24 months post baseline visit to assess for serious adverse events.

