8.4 Primary and Secondary Endpoints

The primary endpoint of this study is the difference between a child's observed and expected changes in GMFM-66 score 12 months after the initial study infusion. This study will provide separate interval estimates of the mean of this outcome measure in patients assigned to the hC-MSC, AlloCB, and Natural History arms at 12-months. The secondary endpoint of this study is the number of adverse events occurring over a 12-month period post-treatment with hCT-MSC or AlloCB.

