9.4 Eliciting Adverse Event Information

In addition to research participant observations, AEs will be documented from any data collected throughout the study including clinically significant laboratory values or physical exam findings.

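### Section 8.1 promises a month-3 adverse-event evaluation in every arm, but the schedule gives month-3 contact and interim blood tests to the MSC arm only

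*Combined protocol and SAP*

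**What the plan says.** Section 8.1 gives the evaluation times: "The occurrence of adverse events will be evaluated at 3, 6, 12, and 24 months post-randomization in all participants".

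The sections that say who is contacted, and when, differ from this at month 3:

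- Section 2.11, on return visits: "They will return for study visits an additional two (AlloCB and natural history arms) or three (MSC arm) times".
- Section 7.1: "Participants on the MSC arm will also return at three months for an hCT-MSC infusion".
- Section 6.6, on in-person checks: "In-person safety assessments will occur at each study visit". On the questionnaire, it "will be administered at 6, 12, and 24 months post baseline visit to assess for serious adverse events".
- Section 7.9: the month-3 column has entries only in the MSC block (history and physical, blood count and metabolic panel, day-after safety check). The rows for all participants, AlloCB and Natural History are empty there. The only remote safety row is at month 24.

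Section 7.4 adds one contact per infusion: "A phone call to parents/guardians by study staff to assess safety of the infusion will be conducted two weeks after the infusion". Sections 6.6 and 7.1 add a check on the day after each infusion.

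The endpoint that depends on these contacts is in section 8.4: "The secondary endpoint of this study is the number of adverse events occurring over a 12-month period post-treatment with hCT-MSC or AlloCB". Section 8.6.1 analyses it as treated in children with at least one infusion, and section 8.6.4 summarises it descriptively by treatment received. Section 9.4 states that "AEs will be documented from any data collected throughout the study including clinically significant laboratory values or physical exam findings".

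**The concern.** Two things follow if the schedule is carried out as written. First, the statistical section describes data that will not exist: no AlloCB or Natural History child has a scheduled adverse-event contact at month 3. Second, the secondary endpoint is a count, and a count rises with the number of occasions on which someone looks. The secondary objective in section 3.0 is the safety of repeated hCT-MSC, and the tables will show hCT-MSC and AlloCB side by side. If one column is fed by an extra examination and extra blood tests, part of any difference in mild or laboratory-detected events may reflect surveillance and not product. Nothing in section 8.6 warns the reader of this or separates the two.

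**Working it through.** **1. The plan's own adverse-event figure.** Section 8.5 gives the probability of seeing at least one event with 30 children per group. The formula is 1 − (1 − p)^30.

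- p = 10%: 1 − 0.90^30 = 95.8%
- p = 5%: 1 − 0.95^30 = 78.5%
- p = 1%: 1 − 0.99^30 = 26.0%

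All three match the plan. They assume that every event that occurs is captured, and capture depends on the contact schedule.

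**2. Scheduled safety contacts after baseline, through month 12** (sections 6.6, 7.1, 7.4, 7.9):

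| | MSC | AlloCB |
|---|---|---|
| Infusions | 3 | 1 |
| Day-1 and week-2 checks | 3 × 2 = 6 | 1 × 2 = 2 |
| Checks per infusion | 2 | 2 |
| Visits with history and physical | 3 (months 3, 6, 12) | 2 (months 6, 12) |
| Post-baseline blood count and metabolic panel | 3 (months 3, 6, 12) | 1 (month 12) |

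The infusion-linked checks are equal per infusion. The excess beyond them is 3 − 2 = 1 visit and 3 − 1 = 2 laboratory sets. The footnote to 7.9 that lets assessments fall within a month of the time point cannot turn a month-6 visit into a month-3 contact.

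**3. Longest interval without scheduled contact** (week 2 taken as 0.5 month). An AlloCB child goes from week 2 to month 6, which is 6 − 0.5 = 5.5 months. Over the same period an MSC child has intervals of 3 − 0.5 = 2.5 months and 6 − 3.5 = 2.5 months.

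**4. The as-treated AlloCB group.** Natural History children receive AlloCB at month 12 and, on the as-treated definition, then count as AlloCB-treated. Their later contacts are day 1, week 2 and the remote assessment at month 24 (timed from baseline, as in 6.6 and 8.3). The interval between the last two is 24 − 12.5 = 11.5 months, with no visit and no laboratory set. With 30 per arm, up to 30 of 30 + 30 = 60 AlloCB-treated children would have this thinner follow-up.

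**5. What unequal capture could do.** The documents give no capture rates, so this only illustrates the mechanism. With equal true rates and an assumed 90% capture in MSC, the observed MSC-to-AlloCB count ratio is 0.90/0.80 = 1.125, 0.90/0.70 = 1.29 or 0.90/0.60 = 1.50 for assumed AlloCB capture of 80%, 70% or 60%. The 95.8% above becomes 1 − (1 − 0.10 × 0.8)^30 = 91.8% at 80% capture and 84.4% at 60%. None of these is an estimate for this trial.

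**The case against.** A reader who adds up all contacts to month 12 finds 9 for MSC, 4 for AlloCB and 2 for Natural History before its infusion, and might infer that MSC is watched 2.25 or 4.5 times as closely. The documents do not support either ratio as a measure of bias. Six of the nine MSC contacts are the same two checks per infusion that AlloCB receives, and they follow from giving three infusions. The comparison with Natural History before infusion lies outside the endpoint, which counts events after hCT-MSC or AlloCB in children who have been infused.

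Three further points stand:

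- The analysis is descriptive, with no test between arms, and the stated objective is the safety of hCT-MSC, not a comparison. Denser observation makes harms of that product easier to see, so any distortion would run against it.
- Section 9.2 requires every reported or observed event to be recorded from enrolment, so an event in month 2 can still be captured at month 6.
- Although section 6.6 describes the questionnaire as aimed at serious events, Appendix 1 also asks about other health problems, skin lesions, new medicines, fatigue, headache, restlessness and tremor since the last visit.

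These points limit the weight of the concern. They do not remove it. Recording whatever is reported schedules no contact, and recall over about five and a half months is weaker than recall over two and a half. Nothing in the documents reconciles section 8.1 with the schedule.

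**Conclusion.** The contradiction is certain: section 8.1 states a month-3 evaluation in all participants, and sections 2.11, 6.6, 7.1 and 7.9 provide it in one arm of three. The effect on the secondary endpoint is a modest ascertainment difference between MSC and AlloCB, arising from one extra visit and two extra laboratory sets by month 12. There is a second difference within the as-treated AlloCB group, where children infused at month 12 have only day-1, week-2 and remote month-24 contacts.

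The size of the effect on the counts cannot be computed, because the documents give no capture rates. It would be too strong to say that the MSC arm will log more events; the text supports only that its count is open to this. The sample size and the primary endpoint are unaffected. The conclusion assumes that the schedule in 7.9 is followed as printed and that Natural History children are pooled with AlloCB once infused, as the as-treated rule implies.

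**What to change.** - **Sections 6.6 and 7.9:** add a remote month-3 contact for the AlloCB and Natural History arms, using the existing Appendix 1 questionnaire and recording all adverse events, not only serious ones. The schedule then matches section 8.1.
- **Section 8.6.4:** put adverse events found only through the MSC-only month-3 and month-6 laboratory tests on a separate line. Show the number of children with at least one event beside the raw count. Show the AlloCB arm separately from Natural History children infused at month 12.
- **If the contact is not added:** correct the sentence in section 8.1 to the times actually scheduled in each arm, and state the unequal ascertainment beside the adverse-event table.

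A split between events found at infusion-linked contacts and events found at common time points is not advised. The MSC visits at months 3 and 6 are both, so the split would not be clean.

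The cost is up to about 30 + 30 = 60 phone or email contacts, an amended schedule table and a few extra table rows, with no new visits or blood draws. About half of the contacts fall in Natural History children before infusion. They make section 8.1 true for all arms but do not feed the post-infusion endpoint. The month-3 contact also leaves the thin follow-up after a month-12 infusion unchanged, which is why those children need their own rows.
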